5. STATISTICAL CONSIDERATIONS

5.A Primary Analyses

Two primary (null) hypotheses have been defined for testing in ACT:

- H₁: there are no differences among the mean levels of VO₂max among persons randomized to the three groups of the clinical trial at 24 months post-randomization, and
- H₂: there are no differences among the mean levels of seven-day self-reported physical activity levels among persons randomized to the three groups of the clinical trial at 24 months post-randomization.

Each hypothesis will be tested according to the intention-to-treat philosophy (Friedman, 1985) in which all randomized participants will be grouped according to their intervention assignment at randomization, regardless of compliance. All primary comparisons will be two-sided (Fleiss, 1987). A Bonferroni adjustment for multiple comparisons will be used to control the Type I error across the two primary hypotheses: individually, each hypothesis will be tested at significance level 0.025. Separate hypothesis tests will be performed on women and men.

General linear models will be used to model the serial data collected on each primary outcome measure. Time since randomization will be grouped by targeted exams (i.e. 6 or 24 month) and parameterized as a fixed class effect. The primary hypotheses will be tested using linear contrasts for interactions between treatment assignment and the indicator variable for the 24 month exam. No *a priori* parametric structure will be assumed for serial correlation. The baseline level of the measure (i.e. VO₂max or seven-day physical activity recall) will be included as a covariate in models, as will terms for the stratification factors: clinical center and race (African-American, Hispanic, Other).

Extensive attempts are planned to promote the retention of ACT participants; however it is expected that not all randomized participants will be evaluated at 24 months. Including interim

data on VO₂max and seven-day physical activity in analyses testing the 24-month differences is expected to reduce the potential biases that may be associated with missing data. This approach allows all participants who have post-randomization measures to contribute to the analysis, and therefore does not exclude persons who are missing 24-month data.

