Secondary analyses will be performed to explore the effect that assumptions about missing data have on trial results. Sensitivity analyses will be conducted in which analysis of results will be performed based on 1) assuming the missing data are missing at random, conditioned on the value of covariates and intermediate results, and 2) assuming that all the unobserved missing data in the intervention and control groups have the same distribution as the observed data in the control group. If these analyses indicate that the results differ substantially, depending on the assumptions one makes about the missing data mechanism, further analyses involving model-based alternatives to the planned primary analyses (e.g. Schluchter, 1992; Shih, 1992; Diggle and Kenward, 1994) and post-hoc stratification (e.g. D'Agostino, 1994) will be explored.

Based on analyses from the Stanford-Sunnyvale Health Improvement Project (SSHIP-I) trial, VO₂max measurements are anticipated to have a right-skewed distribution with the variance increasing with the mean; if this pattern emerges in ACT, a logarithmic transformation will be used, as in the sample size calculations presented below. Each of the three pairwise comparisons of the intervention groups will be tested using a Bonferroni-adjusted significance level of $\alpha=0.0083$ (0.025/3), as is specified in the sample size calculations.

5.B. Secondary Analyses

A series of publications based on the baseline data will be developed to provide the investigators with a first opportunity for a systematic exploration of the central databases; to assist in developing definitions of new variables for future analyses; to begin the development of scientific collaborations; and to cement the protocol for trial publications. Baseline analyses will include descriptions of recruitment, the baseline characteristics of the participants, and cross-sectional analyses of relationships among study variables.

Although the primary hypotheses only address 24-month change, it will be important to examine how the interventions may affect VO₂max and seven-day physical activity recall across the full 24 month period. Secondary analyses will be performed to track these measures across time using mixed effects analysis of covariance models to allow for both time-varying changes in covariates, and varying covariance structures (Laird and Ware, 1982; Jennrich and Schluchter, 1986; Diggle, 1988; Laird, 1992; Wolfinger, 1992).

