Sample size calculations for the ACT trial were based on recruitment of an equal number of participants to each of its three groups. The two primary outcomes in these calculations are logarithmic-transformed VO₂max measurements (unadjusted for weight) and total kilocalorie expenditure per kilogram body weight by seven-day physical activity recall, including light, moderate and heavy activities, but not including sleep. For each primary outcome, the hypotheses to be tested will investigate 24-month differences between all intervention groups; thus a total of six pairwise comparisons will be performed. Preliminary data used for estimating standard deviations of outcomes were obtained from the SSHIP-I trial run by investigators at Stanford University. Based on the SSHIP-I information, we estimated that the standard deviations of log transformed, 24-month VO₂max measurements adjusted for baseline measurements were 0.1214 for men and 0.1215 for women, respectively. Standard deviations for total kilocalorie expenditure were only available for 12 months of follow-up. The 12-month standard deviations of total kilocalorie expenditure were 2.0894 for men and 2.0206 for women, after adjustment for baseline measurements. Sample size calculations were performed separately for men and women.

To ensure an overall, two-sided, Type I error rate, α , of 0.05, each pairwise comparison will be performed at the 0.0083 level (0.05/6), thus using critical regions containing 0.00417 probability in each tail. Assuming equal variances of 24-month outcomes for all intervention groups, the general formula used to determine the appropriate sample size to detect a difference of δ with $1-\beta$ power is

$$N = \left(\frac{1}{r} \right) V \left(\frac{1}{P_1} + \frac{1}{P_2} \right) \frac{(Z_{1-\alpha/2/m} + Z_{1-\beta})^2}{\delta^2},$$

where r is the proportion of participants that will not be lost to follow-up prior to 24 months, V is the baseline adjusted variance of the outcome variable, P_1 and P_2 are the proportion of subjects in the groups being compared, m is the number of trial groups times the number of primary outcomes, and $Z_{1-\alpha/2/m}$ and $Z_{1-\beta}$ are percentiles from a standard normal distribution. For the calculations reported below, we assume 20% loss to follow-up ($r = 0.8$) and have allowed equal numbers in each group. $Z_{1-\alpha/2/6} = Z_{0.00417} = 2.64$ and, for 90% power, $Z_{1-0.1} = 1.282$.

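### The primary VO2max analysis uses the log scale only if a pattern appears in the trial data, although its effect size, SDs and stated power hold on the log scale alone

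*Protocol*

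**What the plan says.** - **Analysis (Protocol 5.A).** The null hypothesis for VO2max is that "there are no differences among the mean levels of VO₂max among persons randomized" to the three groups at 24 months. No scale is given there. Later in 5.A, right skew and variance rising with the mean are anticipated from an earlier trial, and then: "if this pattern emerges in ACT, a logarithmic transformation will be used, as in the sample size calculations presented below".
- **Tests (5.A, 5.C).** "Separate hypothesis tests will be performed on women and men". "All primary comparisons will be two-sided", and "each pairwise comparison will be performed at the 0.0083 level (0.05/6").
- **Sample size (5.C).** "The two primary outcomes in these calculations are logarithmic-transformed" VO2max and energy expenditure from the seven-day recall. Here the log scale carries no condition. The baseline-adjusted log SDs are 0.1214 (men) and 0.1215 (women). The effect is 7%, illustrated as 2000 against 1869 mL/min. The stated power is about 93% in men and 91% in women.
- **Not given anywhere.** The protocol has no SD or power for VO2max on the L/min scale. It sets no threshold for the pattern and does not say what happens if only one of its two features is seen. It also does not say whether baseline or follow-up data are examined, whether they are pooled or split by group, or whether the decision is made once or for each sex.

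**The concern.** Sections 5.A and 5.C treat the same coequal primary outcome differently. For power, the log scale is settled. For analysis, it depends on what the trial data look like. Three things follow.

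1. **Stated power covers one branch only.** If the pattern is judged absent, VO2max is compared in L/min, and the protocol gives no power for that test.
2. **The estimand changes with the branch.** On the log scale the effect is a ratio of geometric means. Untransformed, it is a difference in L/min. Because men and women are tested separately, nothing in the wording stops one sex being reported as a ratio and the other as a difference, and the two could not then be compared directly.
3. **The choice is open to the outcome data.** With no criterion and no blinding stated, the scale could be settled on 24-month results by group. A test chosen that way does not strictly hold its nominal level.

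**Working it through.** **Step 1: what sets the sample size.** The 5.C formula with r = 0.8 and P1 = P2 = 1/3 gives N = (1/0.8) × V × 6 × (2.64 + 1.282)² / δ². For energy expenditure δ = 1.1.

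- Men: 1.25 × 2.0894² × 6 × 15.382 / 1.21 = 416 (stated 417).
- Women: 1.25 × 2.0206² × 6 × 15.382 / 1.21 = 389 (stated 393).

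Using the same formula for log VO2max with δ = ln(1.07) = 0.0677, 90% power needs about 371 men or 372 women. Energy expenditure therefore sets N, and the VO2max scale does not affect it.

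**Step 2: the stated VO2max power.** Power = Φ(δ/SE − 2.638), where SE = SD × √(2/n) and n is the number evaluable per group.

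- Men: n = 417 × 0.8/3 = 111.2; SE = 0.01628; 0.06766/0.01628 = 4.156; power = Φ(1.518) = 93.5% (stated 93%).
- Women: n = 393 × 0.8/3 = 104.8; SE = 0.01678; 0.06766/0.01678 = 4.031; power = Φ(1.393) = 91.8% (stated 91%).

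The stated figures are reproduced on the log scale. The ratio 2000/1869 = 1.070 confirms that the 7% is a ratio.

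**Step 3: what the choice of scale could do.** The documents give no raw-scale inputs, so this step uses assumptions: lognormal VO2max, between-person baseline log SD of 0.20 or 0.30, and baseline slope 0.9 on the log scale. The residual log SDs are the protocol's. Each trial was analysed by ANCOVA on both scales. There were 20,000 null replicates and 5,000 at a true 7% effect.

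Rejection under the null, nominal 0.0083:

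| n per group, baseline log SD | L/min | Log | Pooled skewness rule | Whichever scale rejects |
|---|---|---|---|---|
| 111, 0.20 | 0.0088 | 0.0086 | 0.0086 | 0.0102 |
| 111, 0.30 | 0.0079 | 0.0084 | 0.0084 | 0.0105 |
| 105, 0.20 | 0.0077 | 0.0078 | 0.0078 | 0.0098 |
| 105, 0.30 | 0.0078 | 0.0086 | 0.0086 | 0.0107 |

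The Monte Carlo standard error is about √(0.0083 × 0.9917/20,000) = 0.0006. Each scale alone and the pooled rule are therefore compatible with 0.0083.

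At a true 7% effect:

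| n per group, baseline log SD | Power, L/min | Power, log | Scales disagree |
|---|---|---|---|
| 111, 0.20 | 91.9% | 92.6% | 2.2% |
| 111, 0.30 | 90.4% | 92.8% | 3.9% |
| 105, 0.20 | 90.0% | 91.7% | 3.2% |
| 105, 0.30 | 88.9% | 91.7% | 4.4% |

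A separate run with baseline log SD 0.25, slope 0.85 and 105 per group agrees: 0.0099 if either scale may be picked, power 90.7% (log) against 89.0% (L/min), and 3.3% disagreement.

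**Step 4: the error rate within one sex.** For three equal groups, a normal approximation gives the chance of any false rejection among the three pairwise tests as 0.023 at 0.0083, 0.027 at 0.0099 and 0.029 at 0.0107. Adding the energy-expenditure family (0.023) gives about 0.045, 0.049 and 0.051 to 0.052 across both outcomes, the small range depending on whether the outcomes are independent.

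**The case against.** The strongest reply is that 5.A already names the expected scale, its empirical basis, the trigger and the transformation, and that the threshold, dataset and blinding are ordinary content for a statistical analysis plan. That would be fair if the protocol were silent on the scale. It is not: it states a conditional rule that its own power calculation does not share.

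Several stronger readings are tempting, and the documents do not support them.

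- **That the test is chosen after the outcome is seen.** The text permits this but does not state it. VO2max is also measured at baseline and 6 months, and section 5.D aims to keep investigators blinded, so a check on baseline or pooled data would satisfy the wording. The opposite cannot be assumed either. Under 5.D the Project Office receives unblinded results, and under 7.D the Project Officer votes on the Steering Committee. Nothing says that the scale decision is made blind.
- **That the sample size depends on the log scale.** It does not (Step 1).
- **That type I error is materially inflated.** The figures near 0.010 to 0.011 describe picking whichever scale rejects. The protocol's trigger is distributional shape. Because Bonferroni is conservative for correlated pairwise tests, even that extreme leaves the error within one sex at about 0.05 (Step 4).
- **That the sexes will be analysed on different scales.** The log SDs are almost identical, and the documents give no reason to expect a split. The wording merely fails to rule it out.
- **That H1 contradicts a log analysis.** A null of no effect holds on either scale. Only the reported effect differs.

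**Conclusion.** The point holds as a matter of wording and consistency. The protocol leaves open, for a coequal primary outcome, a choice that its own power statement treats as made. The firm part rests on the documents alone: the 7% ratio, the SDs and the 91% and 93% power hold only on the log scale, and the rule for using that scale has no criterion, dataset or blinding attached.

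The practical size is small. A pooled skewness rule gives essentially no inflation, and the worst case is about 0.010 to 0.011 against 0.0083 per comparison. Disagreement on significance is about 2% to 4% at a true 7% effect, and the log scale gains about 1 to 3 points of power. These figures rest on assumed lognormal data with a baseline log SD of 0.20 to 0.30 and a slope of 0.85 to 0.9, none of which the protocol supplies. The change is worth making because it is free, not because the trial's conclusions are at serious risk.

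**What to change.** Replace the conditional sentence in 5.A with:

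> VO2max and its baseline covariate are analysed on the natural-log scale in both men and women, and effects are reported as ratios of geometric means with confidence intervals.

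Keep the L/min analysis as a sensitivity analysis in both sexes. Align H1 by stating that the comparison is of mean log VO2max. The Summary, section 1.B and section 2.A can keep L/min as the unit of measurement, provided that 5.A is clear about the scale of analysis.

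The cost is a few lines of wording. N stays at 393 women and 417 men, and the stated power of 91% and 93% stands as it is.

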GROUP C: STAFF COUNSELING

This intervention is designed to be an optimal intervention that could be delivered in a primary care setting. It requires substantial staff involvement and employs on-site interpersonal counseling, regular telephone follow-up counseling, in-clinic follow-up counseling, written and visual materials, interactive mail, onsite classes, and referral to community resources.

There will be two primary study outcomes: (1) maximal oxygen uptake (VO_{2max}) ($L \cdot min^{-1}$) measured by a maximal treadmill test using a standardized protocol, and (2) kilocalories expended in physical activity ($kcal \cdot kg^{-1} \cdot min^{-1}$) measured by a standardized and validated self-report instrument, the seven-day physical activity recall. To determine the relative efficacy of the interventions, comparison between groups for mean changes in the outcome measures will be performed. All analyses will be done separately for men and women. Change from baseline to two years will be the primary outcome analysis. Short-term effects will be examined by change from baseline to six months. Secondary outcomes related to cardiovascular disease risk include plasma lipids/lipoproteins (e.g., triglycerides and HDL), blood pressure, body composition (body mass index, skinfolds, waist-to-hip ratio), plasma insulin, fibrinogen, dietary intake, smoking, heart rate variability, cost-effectiveness, and psychosocial factors. Subgroup analyses also will be conducted.

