- a. the effects in sedentary men and women of two primary-care based activity counseling regimens (B and C, representing the staff-assisted and staff-counseling interventions, respectively) on physical activity (defined as energy expenditure) ($\text{kcal}\cdot\text{kg}^{-1}\cdot\text{day}^{-1}$) after 24 months when compared to a Standard Care control (Group A) and to each other; and
- b. the effects in sedentary men and women of the two primary-care based activity counseling regimens (B and C) on cardiorespiratory endurance (defined as maximum oxygen consumption or $\text{VO}_{2\text{max}}$) ($\text{L}\cdot\text{min}^{-1}$) after 24 months when compared to Standard Care control and to each other.

2. Secondary Objectives

Although the primary purpose of ACT is to increase physical activity and cardiorespiratory endurance, a variety of secondary outcomes are important for assessing the effects of the interventions. These include short-term intervention effects, alternate measures of physical activity and fitness, levels of factors related to cardiovascular disease risk, psychosocial factors, and cost-effectiveness. These outcomes may be important for medical care practices to assess their relative enthusiasm for implementing physical activity intervention programs for their patients. In addition, intervention effects in different types of participants are important to assess. The interventions may be successful in some groups but not in others for a variety of reasons such as different perceptions, needs, abilities, or cultural factors.

Secondary objectives are to compare the relative effectiveness of the two primary-care based counseling regimens (Interventions B and C) to each other and vs. Standard Care (Group A) control on:

- a. the effects on physical activity and cardiorespiratory endurance after 6 months;
- b. the effects on submaximal treadmill test performance and shifts from sedentary to light and moderate activity after 6 and 24 months;
- c. the effects on factors related to cardiovascular disease risk (HDL-cholesterol, LDL-cholesterol, total cholesterol, triglycerides, blood pressure, plasma insulin, fibrinogen, body composition, dietary fat intake, smoking status, and heart rate variability) after 6 and 24 months;
- d. the effects on psychosocial factors (mood, self-efficacy, quality of life) after 6 and 24 months;
- e. the relative cost-effectiveness of the two regimens after 24 months;

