- f. the effects after 6 and 24 months by subgroups categorized by the following factors:
 - age
 - ethnicity
 - body mass index
 - medication use (beta blockers or calcium channel blockers)

- smoking status
 - psychosocial variables (mood, self-efficacy, social support); and
- g. the relationship between adherence to the intervention protocols across the initial 6 month and overall 2 year periods and changes in cardiorespiratory fitness, physiological outcomes of interest, and quality of life outcomes.

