Important secondary outcome measures include other measures of fitness and activity, factors related to cardiovascular risk (e.g. levels of lipoproteins, blood pressure, insulin, glucose, and fibrinogen), health related quality of life and cost. Methods similar to those described above will be used for continuous measures. For other types of response variables (categorical, ordered categorical, or counts), we will use the generalized estimating equation (GEE) approach to fit logistic or log-linear models that account for the dependency between repeated measures (Zeger and Liang, 1986; Liang and Zeger, 1986; Prentice, 1988; Zeger, 1988; Lipsitz, 1991; Liang, Zeger and Qaqish, 1992; Miller, 1993). Nonparametric approaches may also be adopted in some settings, as well (e.g. Zerbe and Walker, 1977; Raz, 1988).

A full description of compliance, predictors of compliance, and attrition comprise important

secondary analyses that will allow a more complete understanding of study results. Other important secondary analyses include descriptions of the effectiveness of interventions in pre-defined subgroups formed by race, age, and baseline measures of activity or fitness, body mass index, education, use of beta blockers, pre-existing co-morbid conditions, elevated ST segments, mood disorders, smoking, psychosocial factors and menopausal status. In some secondary analyses, data from women and men may be combined. Cross-sectional and longitudinal relationships among individual outcome measures, and between measures of adherence and outcomes, will also be described.

Importantly, the cross-sectional and longitudinal relationships between VO₂max and other measures of treadmill exercise performance and seven-day physical activity recall will be examined for internal consistency. The robustness of these relationships across study groups and participant subgroups will be assessed using regression analyses.

5.C. Sample Size Considerations

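### The subgroup list in 5.B does not match secondary objective f, the Summary and 5.B disagree on separating the sexes, and describing effects inside each subgroup does not answer whether effects differ between subgroups.

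*Protocol*

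**What the plan says.** Secondary objective f (Protocol 1.B, Secondary Objectives) asks for "the effects after 6 and 24 months by subgroups categorized by the following factors". The factors that follow are age, ethnicity, body mass index, "medication use (beta blockers or calcium channel blockers"), smoking status, and "psychosocial variables (mood, self-efficacy, social support); and". The same section gives the reason for looking: "The interventions may be successful in some groups but not in others for a variety of reasons".

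Section 5.B returns to the subject and plans "descriptions of the effectiveness of interventions in pre-defined subgroups formed by race, age, and baseline measures of activity or fitness, body mass index, education", continuing with "use of beta blockers, pre-existing co-morbid conditions, elevated ST segments, mood disorders, smoking, psychosocial factors and menopausal status". The next sentence adds: "In some secondary analyses, data from women and men may be combined". It does not say which analyses.

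The Summary of the trial states: "All analyses will be done separately for men and women". Section 1.B (Primary Objectives) and sections 2.A and 5.A also call for separation by sex, but there it concerns the primary objectives, outcomes and hypothesis tests.

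**The concern.** Three things on the page do not fit together.

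- A list described as defined in advance should be one list. Here two places in the protocol give two lists, so a later reader cannot tell which subgroups were chosen beforehand.
- Each subgroup result could be produced in men, in women or in both together, and the protocol supports either reading.
- The question in 1.B is about differences in effect between groups. 5.B describes the effect within each group. Set side by side, such descriptions invite the statement that an intervention works in one group and not in another, which a pair of separate results does not establish.

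What is at stake is the credibility and meaning of the subgroup results. The primary conclusions are not at stake.

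**Working it through.** **1. The two lists side by side.**

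| Factor | Objective f | Section 5.B |
|---|---|---|
| Age | yes | yes |
| Race or ethnicity | ethnicity | race |
| Body mass index | yes | yes |
| Beta blockers | yes | yes |
| Calcium channel blockers | yes | no |
| Smoking | yes | yes |
| Psychosocial | mood, self-efficacy, social support | psychosocial factors, not itemised |
| Mood | as a psychosocial variable | mood disorders, listed separately |
| Baseline activity or fitness | no | yes |
| Education | no | yes |
| Co-morbid conditions | no | yes |
| Elevated ST segments | no | yes |
| Menopausal status | no | yes |

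Objective f has six headings, or eight if the three psychosocial variables are counted singly. 5.B has twelve. Five of those have no counterpart in objective f. Mood disorders is a change of definition, not clearly an addition.

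Smoking, body mass index and mood are also secondary outcomes measured again after randomization (4.B, Table 1). Objective f does not say that the groups are formed from baseline values, so the reconciled list should say so.

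**2. Sex.** The Summary covers all analyses. 5.B permits combining in some. Sections 1.B, 2.A and 5.A tie separation by sex to the primary analyses, which suggests that the Summary sentence is the one drawn too widely.

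**3. Is a between-subgroup contrast named?** The only treatment interaction in section 5 is treatment by the 24-month exam, in 5.A, for the primary hypotheses. The regression across participant subgroups at the end of 5.B concerns relationships among outcome measures, not treatment effects.

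**4. The plan's own figure.** The protocol gives no figure for subgroups. Its primary calculation is N = (1/r) V (1/P1 + 1/P2)(2.64 + 1.282)² / δ², with r = 0.8, P1 = P2 = 1/3 and δ = 1.1.

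- Men: 1.25 × 2.0894² × 6 × 3.922² / 1.21 = 416.2 (stated 417).
- Women: 1.25 × 2.0206² × 6 × 3.922² / 1.21 = 389.3 (stated 393).

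Both reproduce closely, and no subgroup enters them.

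**5. Why separate descriptions do not answer the question.** Take women, the SD of 2.0206, and a two-level factor split evenly (an assumption).

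- Completers per arm: 393 × 0.8 / 3 = 104.8, so 52.4 per level.
- SE of a treatment difference within a level: 2.0206 × √(2/52.4) = 0.395.
- SE of the contrast between levels: √2 × 0.395 = 0.558, with 95% half-width 1.96 × 0.558 = 1.09.

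Suppose the estimate is 1.1 in one level and half that, 0.55, in the other. The ratios to the SE are 1.1/0.395 = 2.79 and 0.55/0.395 = 1.39. The first passes the protocol's 2.64 and the second does not. The contrast is 0.55/0.558 = 0.99, which is no evidence of a difference.

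**6. Does an interaction test by itself control chance findings?** The protocol gives no significance level for subgroups, so these figures are conditional. With independent tests and no true effects:

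- one test per factor at 0.05: 1 − 0.95^6 = 0.26 and 1 − 0.95^12 = 0.46;
- twelve factors, three pairs and two outcomes in one sex (72 contrasts): 1 − 0.95^72 = 0.975 at 0.05, and 1 − (1 − 0.05/6)^72 = 0.45 at 0.0083.

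A null simulation used one sex, 324 completers, twelve evenly split factors correlated 0 to 0.4, outcomes correlated 0.2 to 0.5, and 1,500 runs per setting. The chance of at least one false positive at 0.05 was 91–94% for within-subgroup tests and 92–94% for interaction tests. With Bonferroni over the 72 interaction contrasts it was about 4–5%. The contrast therefore answers the right question but does not limit the number of chance findings.

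**The case against.** The strongest reply is that 5.B places this work under secondary analyses and calls it description. It names no test and no significance level, while confirmatory testing is confined to the Bonferroni-controlled primary hypotheses. Error control and an exploratory label are often left to a statistical analysis plan, which may exist. Objective f does not exclude a treatment-by-factor contrast. Both lists were written in advance. Much of this stands: the absence of an error rule is not a finding here, and it would be wrong to say that nothing was pre-specified.

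A reader might infer that false subgroup effects are very likely under this plan. The documents do not support that. The number of tests, the levels per factor, the correlation and the significance level are all assumptions. The computed risk runs from 26% to above 90% depending on them, and large test counts are not properties of the plan.

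A reader might also infer that men and women must be pooled, or that every secondary-outcome analysis must be relabelled. Neither follows. The protocol has a stated reason for looking at the sexes separately, and the other secondary outcomes are not in question.

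The reply does not remove the mismatch between the lists or the conflict over sex. A later analysis plan cannot follow both texts. Nor does the word description make separate subgroup results answer a question about differences.

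**Conclusion.** The point holds in limited form. Two inconsistencies are plain on the page and rest on no assumption: the subgroup lists differ (five factors added, calcium channel blockers omitted, mood redefined), and the Summary conflicts with 5.B on combining the sexes. In addition, what 5.B plans does not match the question posed in 1.B, and a contrast on data already collected would.

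The numerical illustration assumes an even split, the protocol's SD for women (taken from 12-month data) and 20% loss. On those terms a single-sex subgroup contrast has a 95% half-width of about 1.09 kcal/kg/day, about as large as the 1.1 design difference. That is itself a reason to treat the results as exploratory. The primary hypotheses, their error control and the sample size of 393 women and 417 men are untouched. This is a cheap improvement to secondary analyses, not a threat to the trial's main result.

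**What to change.** - Put one subgroup list, with every factor defined from baseline data, in both secondary objective f and 5.B. Settle there whether calcium channel blockers belong, how mood is defined, and whether the five extra factors stay.
- Limit the Summary sentence on separate analysis by sex to the primary analyses. State in 5.B whether the subgroup analyses are by sex or pooled.
- For each factor, report the treatment-by-factor contrast at 24 months with its confidence interval, next to the subgroup estimates.
- Describe these results as exploratory, because interaction tests alone do not control the number of chance findings.

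The cost is wording in three places and a few extra models on data already collected. The downside is that subgroup results could not be presented as confirmatory.

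### Section 5.C claims an overall Type I error of 0.05 over six comparisons, but testing men and women separately makes twelve: the 0.05 holds within each gender, and the trial-wide bound is 0.10

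*Protocol*

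**What the plan says.** Section 5.C (Sample Size Considerations) counts three pairs of groups on two primary outcomes: "thus a total of six pairwise comparisons will be performed". It then fixes the level: "To ensure an overall, two-sided, Type I error rate, α , of 0.05, each pairwise comparison will be performed at the 0.0083 level (0.05/6"). The divisor is defined in the same section: "m is the number of trial groups times the number of primary outcomes". That is 3 × 2 = 6, and gender does not enter.

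Section 5.A (Primary Analyses) splits alpha between the two primary hypotheses: "individually, each hypothesis will be tested at significance level 0.025". It adds: "Separate hypothesis tests will be performed on women and men". It then gives the pairwise rule, "Each of the three pairwise comparisons of the intervention groups will be tested using a Bonferroni-adjusted significance level of" 0.0083, which is 0.025/3.

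Sections 1.B and 2.B (Inclusion of Women and Minorities) say that the primary objectives are addressed separately in the two genders and that the trial was sized separately in each for that purpose. No section says that the 0.05 applies within a gender, and none adjusts for testing in two genders.

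**The concern.** The number of primary pairwise tests is 3 pairs × 2 outcomes × 2 genders = 12, not six, and each is done at 0.0083. A significant result in either gender would be reported as a primary finding. Someone who takes 5.C at its word would believe that the chance of any false primary claim in the whole trial is at most 5%. With twelve tests at that level it can be close to twice that.

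A separate and lesser matter is efficiency. A single-step Bonferroni correction over the three pairs is valid but stricter than three groups require. That costs power for the conclusions that need more than one pairwise rejection, and for B versus C, which section 1.B makes part of the primary objectives.

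**Working it through.** **Inputs (protocol 5.C and 5.A).** Level per comparison 0.05/6 = 0.025/3 = 0.00833. Baseline-adjusted SD of energy expenditure 2.0894 (men) and 2.0206 (women); difference to detect 1.1 kcal/kg/day. SD of log VO2max 0.1214 (men) and 0.1215 (women); difference 7%. Loss to follow-up 20%, equal allocation, N = 417 men and 393 women.

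**1. The plan's own figures.**
- z for two-sided 0.00833 = 2.638 (protocol: 2.64).
- N per gender = (1/0.8) × SD² × (3 + 3) × (2.64 + 1.282)² / 1.1².
- Men: 416 (stated 417). Women: 389 (stated 393).
- Power for 1.1 kcal/kg/day at the stated N: 90.1% men, 90.4% women (stated 90%).
- Power for VO2max at log(1.07): 93.5% men, 91.8% women (stated about 93% and 91%).

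Alpha, sample size and power agree with one another when the family is six tests in one gender.

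**2. Error within one gender.**
- Bonferroni bound: 6 × 0.00833 = 0.05.
- If the six tests were independent: 1 − (1 − 0.00833)^6 = 0.049.
- The three contrasts share arms, so the real figure is lower. A simulation (3 million draws) at an assumed correlation between the two outcomes of 0, 0.3, 0.5 and 0.8 gives 0.045, 0.044, 0.043 and 0.037.

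The 0.05 therefore holds within each gender.

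**3. Error across both genders.** Men and women are different participants tested separately, so the two sets of results are independent: trial-wide error = 1 − (1 − p)², where p is the error in one gender.
- Bonferroni bound over twelve tests: 12 × 0.00833 = 0.10.
- If each gender used its full 0.05: 1 − 0.95² = 0.0975.
- With the simulated p: 0.088, 0.087, 0.084 and 0.073 at outcome correlations 0, 0.3, 0.5 and 0.8.
- Limiting case of two identical outcomes (correlation 1): 0.045.

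The protocol gives no correlation between the outcomes, so only the 0.10 bound is free of assumption.

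**4. The step-down option.** With three groups, once one pairwise null hypothesis is false, at most one of the other two can be true. After one rejection at 0.0083, the other two can therefore each be tested at 0.025 while the error stays at 0.025 for that outcome and gender. Simulated error: 0.023 with all three nulls true, 0.025 with exactly one true.

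Simulated power on energy expenditure at the stated N, SD and loss:

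| Assumed scenario | Claim | Single-step | Step-down |
|---|---|---|---|
| B and C both 1.1 above A, men | both beat A | 83% | 91% |
| Same, women | both beat A | 84% | 91% |
| C 1.1 above A, B midway (0.55) | B versus C | 25% | 38–39% |

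Both scenarios are assumptions. The protocol states power for a single pairwise difference of 1.1 and for nothing else.

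**The case against.** The strongest reply is that the per-gender family is deliberate and can be read from the text. In 5.C, the sentence just before the claim of overall control says that the sample size calculations were done separately for men and women. Sections 1.B and 2.B pose the question separately in each gender, and 5.B pools them only in some secondary analyses. Giving two disjoint populations their own 0.05 is a recognised choice, and under it every figure in 5.C is consistent. This stands. It means that the level is defensible and that only the words describing it are wrong. The protocol nowhere says *within each gender*, while it does say *overall* and *a total of six*.

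Three stronger readings are tempting and are not supported:

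- *The alpha or sample size is miscalculated, and the level should be 0.05/12.* The figures reproduce. Twelve-fold control would need about 465 men and 435 women for 90% power, or would leave about 86% power on energy expenditure at the stated N. The documents do not set that aim, and this review does not ask for it.
- *The trial-wide error is 0.09.* That figure depends on a correlation that the protocol does not give.
- *Single-step Bonferroni is an error.* It is valid, prespecified, the same in 5.A and 5.C, and matched to the sample-size formula. The protocol never claims power for both interventions jointly beating Standard Care, so the 83% contradicts nothing. Step-down testing is an offer of efficiency only.

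**Conclusion.** The point holds as a misstatement of scope in 5.C. Twelve primary pairwise tests are planned, not six, and the 0.05 is controlled within each gender, not over the trial. The trial-wide chance of at least one false primary claim is at most 0.10, and about 0.07 to 0.09 if the correlation between the two outcomes lies between 0.8 and 0 (an assumed range). It would fall below 0.05 only if the outcomes were nearly identical, which is not expected of self-reported activity and measured fitness. The design itself need not change.

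The step-down rule is a separate, valid improvement that needs no extra participants. Its gains are about 8 percentage points for showing that both interventions beat Standard Care and about 13 points for B versus C, under the assumed effect patterns on energy expenditure.

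**What to change.** **(a) Wording, needed.** In 5.C, replace *overall* with *within each gender*, and *a total of six* with *six in each gender (twelve in all)*. State that the trial-wide error is bounded by 0.10, and word primary conclusions by gender. Section 5.A does not use *overall* for the error rate, so it needs no such correction. Cost: text only. Alpha, sample size and stated power stay as they are; the stated trial-wide rate becomes less favourable.

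**(b) Step-down testing, optional.** In 5.A, within each outcome and gender: if the smallest of the three pairwise p-values is below 0.0083, test the other two at 0.025. Cost: this changes the primary testing rule and so is more than a wording change. The Bonferroni-level intervals (99.17%, that is 1 − 0.05/6) may include zero when the step-down test rejects with p between 0.0083 and 0.025. The report should say that tests and intervals can disagree in that range.
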